Cochlear implantation has been reported as a viable treatment option in cases of unilateral hearing loss, including sudden sensorineural hearing loss (Firszt et al, 2012), and severe tinnitus (Vermiere & Van de Heyning, 2009; Van de Heyning et al, 2008). Further, cochlear implantation has been shown to offer superior speech perception in noise, localization abilities, and subjective report in SSD cases as compared to CROS hearing aids and bone-conduction devices (Arndt et al, 2011). The limitation to this comparison, however, was the subjects had limited listening experience with the alternative treatment options (i.e. CROS hearing aids or bone-conduction device). Though other studies reported no difference in abilities with these technologies after 4 weeks of listening experience (Bosman et al, 2003), long-term duration of listening experience may influence speech perception and localization abilities. Considering this, a control condition of long-term users of current treatment options (i.e. bone-conduction devices) may provide a more accurate comparison with SSD cochlear implant recipients.

The primary goal of this project is to determine whether subjects with SSD experience an improvement in speech perception, localization, and quality of life with a cochlear implant as compared to an unaided listening condition. Secondary aims include: 1) a comparison of speech perception, localization, and quality of life outcomes in the study population to a SSD control group with long-term listening experience with a current treatment option (i.e. bone-conduction device), and 2) a within-subject comparison of speech perception and localization abilities with cochlear implantation versus the bone-conduction test device.

III. Objectives

- A. The primary purpose of this feasibility study is to demonstrate the effectiveness of cochlear implantation in subjects with SSD
 - 1. Postoperative results will be evaluated with speech perception measures, localization tasks, and subjective reports

- B. Compare outcomes of cochlear implantation to that of current treatment options (i.e. bone-conduction devices) for SSD cases
 - 1. Compare speech perception, localization, and subjective outcomes to a control group of implantable bone-conduction device recipients
 - 2. Assess cochlear implant subjects with a bone-conduction test device and/or previous BAHA device at the preoperative and 12 month follow-up intervals

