 - a. Comparison of individual subject speech perception and localization abilities between the cochlear implant and bone-conduction device

IV. Definitions

Adjusted Constant Error: the rms deviation of the mean responses from the diagonal, computed after compensating for bias. This procedure reduces the bias when evaluating the relationship between the average response on the azimuth and signal source on the azimuth.

Bimodal: Cochlear implant in one ear and a conventional hearing aid in the contralateral ear

Bone-Conduction Device: A device on the poorer hearing ear that picks up the acoustic signal on the effected side and transmits to the better hearing ear via vibrations through the skull. This is accomplished by either securing the oscillator to the head with a headband or via a percutaneous, implanted titanium abutment.

Cochlear Implant (CI): A two-part system, including the internal electrode array and external speech processor that stimulates the auditory pathway on the effected side. The internal electrode array is surgically implanted into the affected cochlea. The external speech processor receives sounds and transmits this signal to the internal portion. The electrode array presents the acoustic signal via electrical pulses within the cochlear space, which is interpreted by the brain as sound.

Constant Error: the rms deviation of the average responses from the source positions

Contralateral Routing of Signal (CROS) Hearing Aids: A two-part system consisting of a transmitter microphone on the deafened ear and a receiver on the normal hearing ear. The transmitter sends the signal from the deafened ear to the normal hearing ear. The auditory pathway on the normal hearing ear receives the sound.

Interaural Level Difference (ILD): The difference in sound level between the two ears, dependent on the location of the sound source and the orientation of the head. This binaural cue is typically dominated by high frequencies.

Interaural Timing Difference (ITD): The difference in the time a sound arrives to one ear as compared to the other, dependent on the location of the sound source and the orientation of the head. This binaural cue is typically dominated by low frequencies.

Pure Tone Average (PTA): The average threshold (dB HL) from 500, 1000, and 2000 Hz

Random Error: the standard deviation of responses at each signal source position, averaged across all potential signal sources

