 - ii. Can be less than or equal to 10 years if the subject consistently utilized hearing technology (such as a bone conduction device or conventional hearing aid) within the past 5 years
 - d. Previous experience with a current treatment option for SSD, including a conventional hearing aid, bone-conduction device, or CROS/BICROS technology.
 - i. At least one month of listening experience with device
 - ii. Dissatisfaction with and/or discontinued use of current treatment option due to: insufficient gain, poor sound quality, and/or lack of perceived benefit.
 - e. Aided word recognition in the ear to be implanted of 60% or less as measured with CNC words (50-word list)
 - i. When listening with an appropriately fit hearing aid and masking applied to the contralateral ear
 - ii. Aided testing will be conducted in a sound-proof booth with the subject seated 1 meter from the sound source, facing 0° azimuth. Recorded materials will be presented at 60 dB SPL.
 - iii. The hearing aid output will be measured using NAL-NL1 targets.
 - f. Realistic expectations: a verbal acknowledgement of the potential benefits and risks, and postoperative variation in performance. For instance, cochlear implantation will not restore normal hearing
 - g. Willing to obtain recommended meningitis vaccinations per CDC recommendations
 - h. No reported cognitive issues
 - i. Pass the Mini Mental State Examination (MMSE) screener
 - i. Able and willing to comply with study requirements, including travel to investigational site and study-related activities
- 2. Exclusion Criteria
 - a. Non-native English speaker
 - i. Speech perception materials are presented in English
 - b. Conductive hearing loss in either ear

- c. Compromised auditory nerve, including those with a history of vestibular schwannoma
- d. Ossification
- e. Inability to participate in follow-up procedures (i.e., unwillingness, geographic location)
- f. History of meningitis, autoimmune disease, or any medical condition that contraindicate middle or inner ear surgery or anesthesia
- g. Meniere's disease with intractable vertigo
- h. Trauma that precludes inner ear surgery
- i. Case of sudden sensorineural hearing loss that has not been first evaluated by a physician
- j. Pregnancy
 - i. Subjects who are pregnant or become pregnant prior to surgery are excluded due to the potential risk of anesthesia to an unborn child.
 - a. Subjects who become pregnant after surgery may continue to participate in study procedures

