 - 1. Subjects will participate in two aural rehabilitation sessions with a board-certified speech-language pathologist. One session will be after the initial activation of the external speech processor. This will occur either on the same day as the initial activation or within the first 2 weeks of listening experience. The second session will be scheduled in conjunction with the 1-month post-initial activation interval.

VIII. Proposed Claims

- A. Demonstrate the effectiveness of cochlear implantation in SSD subjects
 - 1. Demonstrate an improvement in speech perception abilities, localization, and/or subjective benefit in an aided (cochlear implant on) versus an unaided (cochlear implant off) condition
- B. Cochlear implantation provides similar or superior speech perception, localization, and/or quality of life as compared to that found with bone-conduction devices
 - 1. Comparison with control group performance
 - 2. Comparison within subject when listening with bone-conduction test device

IX. Statistical Analysis

- A. Descriptive summaries will be provided for the following: subject demographics, and frequency of major and minor complications/adverse events.
- B. A single-subject design will be utilized, where each subject serves as his or her own control, for analysis of objective and subjective results. A single-subject design was chosen in order to accommodate the heterogeneity that is well known to characterize auditory prosthesis research. Repeated-measures ANOVA will be calculated with a p-value of ≤ 0.05 for statistical significance. Statistical analysis will be conducted with SPSS software.
 - 1. Comparison of aided speech perception performance on word and sentence materials in the post-initial activation intervals to evaluate trends over time

- a. Comparison of the difference between the aided and unaided conditions at each follow-up interval
- 2. Comparison of localization abilities in the post-initial activation intervals
 - a. Comparison of the difference between the aided and unaided conditions for each follow-up interval
 - b. Compute the overall rms error, random error, constant error, and adjusted constant error, as described by Grantham et al (2007)
- 3. Comparison of subjective report scores in the post-initial activation intervals

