 - 3. Reports of pain from the external speech processor placement will be addressed by different wearing options (i.e. moleskin between the external speech processor and the subject's ear, or different battery-wearing options to lighten weight on the pinna).
 - 4. Mapping will be conducted at each post-initial activation interval to improve audibility and comfort of the sound quality from electric stimulation.
 - 5. The MED-EL cochlear implant has MRI limitations*. Subjects may have CT scans or x-ray imaging postoperatively when warranted.
 - a. *The MED-EL CONCERT cochlear implant is approved for MRI of 0.2 or 1.5 Tesla
 - 6. An otologist will conduct medical follow-up evaluations at the 6 and 12-month intervals, which is standard of care for cochlear implant recipients.
 - 7. Age appropriate vaccinations per the CDC recommendations will be completed by each subject prior to implantation. Subjects will be counseled regarding meningitis vaccinations and directed where to obtain them by their implanting physician.

XII. Potential Benefits

- A. Improvement in speech perception abilities in noise with the cochlear implant due to utilization of auditory cues from both ears.
- B. Improvement in localization abilities with the cochlear implant due to utilization of auditory cues from both ears.
- C. Improvement in subjective benefit with the cochlear implant as compared to preoperative performance.

The potential benefits of cochlear implantation in cases of SSD are suspected to outweigh the risks listed in Section XI.A. The study sample will include subjects with previous history with current hearing technology options for SSD, who are dissatisfied with this technology and/or have discontinued use of the technology. This sample is similar to those in previously published reports who have benefited from cochlear implantation.

This study also includes a comparison to a currently approved technology option for SSD, boneconduction technology. This comparison will be used to assess outcomes between technologies, but also to determine whether individual subjects experience differences in performance between the two technologies. The risks associated with cochlear implantation in this population are also reduced considering subjects may continue to use currently approved technologies for SSD if they do not obtain subjective and objective improvements from cochlear implantation.

XIII. Adverse Events

- A. Anticipated versus Unanticipated Events

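### Claim VIII.B allows 'similar' to bone conduction, but the only stated rule is a difference test; the control-group analysis is not stated and the within-subject contrast is not listed

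*Combined protocol and SAP*

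**What the plan says.** Section VIII.B proposes that "Cochlear implantation provides similar or superior speech perception, localization, and/or quality of life as compared to that found with bone-conduction devices". It lists two supporting comparisons: with the control group (B.1), and within subject using the bone-conduction test device (B.2).

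The data for both are planned. Objective III.B names both comparisons. For the second it says "Assess cochlear implant subjects with a bone-conduction test device and/or previous BAHA device at the preoperative and 12 month follow-up intervals", followed in III.B.2.a by "Comparison of individual subject speech perception and localization abilities between the cochlear implant and bone-conduction device". Section XII repeats the aim: "to determine whether individual subjects experience differences in performance between the two technologies". Section VI.B.2 gives the control group one evaluation. Section VII.C.4.g adds the bone-conduction condition at 12 months, and Appendix A shows it preoperatively and at 12 months.

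Section IX.B sets the inferential approach: "A single-subject design will be utilized, where each subject serves as his or her own control, for analysis of objective and subjective results", and "Repeated-measures ANOVA will be calculated with a p-value of ≤ 0.05 for statistical significance". The items listed under it compare the implant on with the implant off, or follow scores across the post-activation intervals. Section IX.C covers interference between the ears. Section IX mentions neither the control group nor the bone-conduction condition.

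**The concern.** A test for a difference can show that one device is better. Failing to find a difference does not show that two devices are alike, least of all in small samples. *Similar* needs a criterion, such as a margin that the confidence interval must exclude, and none is given. It would therefore have to be defined after the data are seen.

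The two comparisons also stand differently in Section IX. Controls are independent people tested once, so an own-control design cannot cover them, and no group factor or between-group test is stated. B.2 is an own-control comparison, so the general method could apply, but nobody reading Section IX would know which contrast, at which visit, decides the claim.

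At stake is what the report may say about the implant against an existing treatment option.

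**Working it through.** **The plan's own figure.** The cohort of 20 is said to allow for about 20% dropout: 20 × 0.80 = 16 completers. Only that step can be reproduced, because Section IX gives no effect size, SD, power or margin. The control group is *at least 10* (VII.B.3), with no derivation.

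**Inputs.** 16 or 20 implant subjects; 10 controls; two-sided 0.05 (the plan does not state sidedness). No SD is documented, so results are in SD units. Effect sizes, equal SDs and normal data are assumptions. Probabilities come from the noncentral t distribution.

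**B.1, between groups.** SE = √(1/n₁ + 1/n₂); half-width = t(0.975, df) × SE.
- 16 v 10: SE = √(1/16 + 1/10) = 0.4031, df 24, half-width 2.064 × 0.4031 = 0.83 SD. If the implant is truly 0.8 SD worse, noncentrality is 0.8/0.4031 = 1.98 and P(not significant) = 0.522.
- 20 v 10 (no dropout): SE 0.3873, df 28, half-width 0.79 SD, P(not significant) = 0.486.
- 16 v 20: half-width 0.68 SD, P(not significant) = 0.360. Twenty controls is purely an assumption; the documents give only the minimum of 10.

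**B.2, pairs.** SE = 1/√n, in units of the SD of differences, which is a different scale from B.1.
- 16 pairs: SE 0.25, df 15, half-width 2.131 × 0.25 = 0.53. A deficit of 0.5 is missed with probability 0.535, and one of 0.8 with probability 0.152.
- 20 pairs: half-width 0.47; the same deficits are missed with probability 0.436 and 0.076.

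**Power for *superior*** at true advantages of 0.5, 0.8 and 1.0:
- 16 v 10: 22%, 48%, 66%.
- 16 pairs: 46%, 85%, 96%.

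**Multiplicity.** VIII.B joins its three domains by *and/or*, and VII.D has several speech materials and noise positions. With five independent measures, no true difference and one-sided 0.025 each, the chance of at least one false *superior* is 1 − 0.975⁵ = 0.119, about 12%. Five is illustrative; correlated measures would give less.

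**Quality of life.** III.B.2.a covers speech perception and localization only. Appendix A lists sound-field measures, and no questionnaire, under the bone-conduction condition. This part of the claim therefore rests on B.1 alone.

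**The case against.** The strongest reply is that IX.B applies the own-control ANOVA generally to objective and subjective results, so B.2 already has a method. That largely stands. A reader might infer that neither comparison has any test, but the documents support that only for B.1. For B.2, what is missing is the listed contrast and its time point. Repeated-measures ANOVA could also carry a group factor for B.1, but none is stated.

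A reader might also infer that the plan will report a non-significant result as *similar*. No passage says so. What stands is that no other criterion is offered.

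Third, III.A calls this a feasibility study, the bone-conduction comparison is a secondary aim, and statistical consultation is available if needed. All true, and it limits the weight of the point. But VIII.B is a proposed claim for which a control group is recruited and a test condition added, and possible consultation is not a decision rule.

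Fourth, the protocol expects the implant to do better: its background text, just before Section III, cites an earlier comparison in which "cochlear implantation has been shown to offer superior speech perception in noise, localization abilities, and subjective report in SSD cases". An implant 0.8 SD worse is therefore an illustration, not a forecast. The interval widths do not depend on it.

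Finally, a reader might infer from the eligibility differences that B.1 is biased in a known direction. The documents do not support that. Implant subjects must report "Dissatisfaction with and/or discontinued use of current treatment option", face a tinnitus-score exclusion, and may have up to 10 years of hearing loss if they used hearing technology. Controls are limited to 5 years at BAHA implantation, but then need at least 12 months of use with no upper limit, so their total duration at testing could be longer. Long-term users were chosen on purpose.

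**Conclusion.** The point holds in this form: B.1 has no stated analysis, the B.2 contrast is not listed, and the one stated rule can support *superior* but not *similar*, which is undefined. With 16 v 10, a non-significant result would leave differences within about ±0.83 SD of the estimate open; with 16 pairs, within ±0.53 SD of differences. A 0.8 SD deficit would be non-significant 52% of the time in the first case. In the second, a deficit of 0.5 SD of differences would be missed 54% of the time. These figures assume the stated 20% dropout, the minimum control group, equal SDs and normal data; the effect sizes are not from the documents.

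The consequence arises only if *similar* is claimed. It does not extend to the primary effectiveness endpoint in Section X, which compares the implant on with off. The plan should be changed before analysis, but the point does not undermine the study.

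**What to change.** Restrict VIII.B to superiority, or to estimated differences with 95% CIs, and state that a non-significant difference will not be reported as *similar*. For any *superior* claim, name one key measure per domain in advance, or set a multiplicity rule. Because AzBio in noise changes its SNR with the score (VII.D.3.b), compare those scores only at a common SNR, or make BKB-SIN the key noise measure.

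Add two entries to Section IX:

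- **(a)** Implant results at 12 months against the control group's single evaluation, as a difference with 95% CI, labelled non-randomized, with the eligibility differences listed for both groups. State that the quality-of-life comparison rests on this entry alone.
- **(b)** A paired 12-month contrast of implant with bone conduction, with 95% CI, for speech perception and localization, plus the individual results called for in III.B.2.a. Report each subject's device (headband or own BAHA) and the preoperative bone-conduction data. State that bone-conduction experience may be far shorter than a year of implant use, a limitation the background text itself raises about an earlier comparison.

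The cost is wording in VIII.B and two entries in IX, using data already scheduled. The claim becomes less favourable, and between-group power for superiority is modest, as shown above.

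Keeping *similar* costs more. It needs margins set before analysis, which the documents do not supply, and a 95% CI that excludes the margin on the side where the implant is worse. With no true difference, 16 v 10 would have 22% or 48% power at assumed margins of 0.5 or 0.8 SD; 16 pairs would have 46% or 85% on the SD-of-differences scale.
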